#### Loss of confidentiality

The research team has established procedures in place to minimize the risk of any confidentiality breach. Participant records are stored in locked files within locked offices in areas that are locked during holidays, weekends, and non-working hours. Information contained in computer databases is password protected, maintained by participant number only, and devoid of specific identifiers. No specific or general participant information will be left in public access areas, and no oral communication regarding participants with identifiers will be made in any public areas. Research staff members have been given extensive training in maintaining confidentiality as well as HIPAA regulations.

#### Nicotine withdrawal

This study involves a three-day period of abstinence. Participants will be asked to remain abstinent for a total of 72 hours. Participants will be daily smokers, and as such, they may experience tobacco/nicotine withdrawal symptoms and/or discomfort during this time. Tobacco withdrawal symptoms may include anxiety, depressed mood, irritability, restlessness, sleep difficulty and strange dreams, increased appetite/weight gain, headaches, tension, difficulty concentrating and general physical discomfort. There are no reports in the current literature of severe physiological or psychiatric consequences resulting from tobacco withdrawal. Participants will be informed of the potential discomfort they may experience during this brief period of abstinence and will be advised to contact research staff if they feel that their withdrawal symptoms worsen during the 72-hour period.

#### Absence of Coercion

Participation in the study is voluntary. Participants will be compensated \$20-50 for each successfully completed visit and up to \$140 for abstinence during Days 1-3 of the study protocol. Participants will be eligible for a maximum of \$594.

The informed consent agreement that will be read to each participant prior to enrollment in the study explains the following:

- a. Compensation will be paid at each study visit.
- b. Participants may discontinue participation in the study at any point.
- c. Withdrawing from the study will not result in any adverse consequences to the participants.

### b. Protection against Risk

Research staff will closely supervise participants throughout their enrollment in the study.

- a. Loss of confidentiality: Paper-based information will be kept in on-site locked file cabinet(s) designated for study materials. Data collection instruments or forms containing participant names will be stored in

separate secure locations from those instruments or forms containing subject identification (SID) numbers, and both will be stored separately from the master list linking the SID and names. Paper-based information will be accessible only to study personnel who need access to the information for study purposes. All electronic records will be stored on a password protected secure server with access limited only to study personnel who need access to the information for study purposes.

b. **NAC:** Exclusion criteria are crafted to exclude potential participants at higher risk for adverse effects, including those taking medications with known metabolic interactions with NAC. We will also monitor vital signs and adverse events during weekly medication monitoring visits. Participants will have access to a medical doctor 24 hours, 7 days a week for emergencies. Urine pregnancy tests will be done for female participants before study inclusion and at every study visit during the medication phase (Weeks 1-8). Serious adverse events will be reported to the local IRB, the sponsor, and the FDA.

### 3. POTENTIAL BENEFITS OF THE PROPOSED RESEARCH TO THE SUBJECTS AND OTHERS

There may not be direct benefits of this study to participants, though they may reduce or quit smoking with the experimental pharmacotherapy. We are primarily assessing the feasibility of conducting a trial of NAC in cigarette smokers, though we will also explore the clinical effects of this pharmacotherapy on initial abstinence and relapse prevention. Participation in the study may greatly benefit future inquiry into pharmacotherapy for smoking cessation and improving upon FDA-approved medications.

### 4. IMPORTANCE OF THE KNOWLEDGE TO BE GAINED

This study will inform the clinical treatment of smoking by providing preliminary feasibility and efficacy data for NAC for tobacco use disorder in adult, daily smokers. This study will also help to inform clinicians as to how best NAC should be used for smoking cessation (initial cessation aid, relapse prevention aid, or both). These data are vital to further explore the potential efficacy of NAC in promoting abstinence and relapse prevention in a larger, double blind randomized controlled trial.

### 5. SUBJECT SAFETY AND MINIMIZING RISKS (Data and Safety Monitoring Plan)

All aspects of the study will be run through the MUSC Department of Psychiatry and Behavioral Sciences, where the PI holds an appointment. Consistent with the guidelines of the MUSC IRB, an internal Data and Safety Monitoring Plan (DSMP) will be used. An internal DSMP is appropriate for this trial because: 1) it does not involve a large number of subjects, 2) it does not involve a multi-site trial, and 3) it presents minimal risks to patients.

Guidelines have been developed for managing and reporting of SAEs. [name] (PI) and [name] (Co-I) will work as a team to serve as the Program Manager for SAEs. The Adverse Event (AE) Log will be used to document all AEs. If an AE is non-serious (self-limited with no intervention needed), no further action will be necessary. However, in the case of an SAE (unresolved event), an AE follow-up log will be completed. The clinician will then call [name] and [name] with initial reports within 24 hours of the start of AE. The clinician will record the information on SAE Notification Form. He/she will forward hard copies of the complete report (SAE Notification Form, Concomitant Medication Log, and AE Log) to [name], who will, in turn notify the IRB about the SAE. If the event is "Serious, Unexpected and Associated," [name] will complete Food and Drug Administration (FDA) Form 3500A and will forward it to the FDA. [name] and/or [name] also will inform the IRB and the study participants about the SAE. In all of these reviews and reports, strict patient confidentiality will be maintained.

Trained research staff will assess any adverse events and will consult with a medical clinician to assess the severity, relatedness, and if further action is required. Clinical stability and medication side effects will be assessed at each study visit during the medication trial. Study medication may be discontinued at any time due to adverse experiences or marked deterioration. A member of the research team and/or the Department of Psychiatry on-call team will be available by pager at all times. Dosage may be decreased at any time. Participants who are experiencing intolerable side effects will be advised to contact a study physician to discuss whether a dosage reduction is indicated. The dose will not be decreased prior to consultation and approval by a study physician. At the end of the study, participants will be referred to the clinician of their choice (primary care or other practitioner) for continued treatment for nicotine dependence.

Circumstances requiring that a patient be terminated from the study are as follows: (1) Development of intolerable side effects not responsive to dosage reduction (though we will encourage participants to remain in the study without medication). (2) Development of physical illness, which would preclude medication ingestion. (3) Development or exacerbation of a psychiatric condition such as suicidal ideation with a plan or onset of psychotic symptoms, which would normally require medication or other therapeutic intervention such as hospitalization. (4) Emergence of another substance abuse problem that needs more intensive treatment (hospitalization). (5) Incarceration for one week or more during the study. (6) Failure to report for medication assessment within fourteen days of the scheduled visit. (7) Pregnancy. In all cases, the research team will make every effort to manage the participant and collect appropriate adverse event outcome data.

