#### Statistical Analyses

Categorical clinical and demographic variables will be assessed by chi-square tests of independence, while continuous variables will be assessed using Student's *t*-test. In addition to baseline group differences, preliminary analysis of baseline characteristics with tobacco use outcomes of interest will examine significant correlates of abstinence in the study population. Characteristics found to be significantly associated with tobacco abstinence and relapse outcomes will be included as covariates in the initial stages of model development. The primary measure of interest will be the proportion of biochemically confirmed and self-reported 3-day abstinence (defined as twice per day breath CO measures of  $\leq 6$  ppm or a 75% reduction from the participant's averaged baseline and Day 0 CO samples). The proportion of participants achieving 3-day abstinence will be compared between NAC and placebo treatment groups using logistic regression models (Specific Aim #1). Secondarily, there is great interest in determining if those who achieved 3-day abstinence under NAC treatment were less likely to relapse over the course of eight weeks compared than those who achieved abstinence under placebo treatment (Specific Aim #2). Daily smoking diary data will be used in conjunction with weekly breath CO measures to determine if and when relapse to regular smoking returned during the eight weeks of treatment with the study drug. Based on recommendations for defining treatment failure, relapse will be defined as smoking during seven consecutive days or smoking at least once over two consecutive weeks (54). This definition will account for regular and irregular smoking over the course of the eight-week intervention phase. Cox proportional hazards models will be developed to assess the efficacy of NAC in prolonging abstinence and preventing relapse. Additionally, end of study 7-day point prevalence abstinence will be assessed through the proportion of self-reported and biochemically confirmed 7-day abstinence. Biochemical confirmation for end-of-study abstinence is defined as a negative daily breath CO measures ( $\leq 6$  ppm or 75% reduction from baseline) and a negative urine cotinine measure ( $<80$  ng/mL). The main effect of NAC versus placebo on the proportion of abstinent participants will be assessed using logistic regression models. All stated models will be computed both unadjusted and adjusted for significant covariates and confounders found in the preliminary analysis. All randomized participants will be included in the primary analysis (intent-to-treat; ITT) and participants will be deemed not-abstinent at any missed visit or missing CO measure (drop-out/loss-to-follow up included). In addition to the primary ITT analyses,

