We will aim to recruit 110 enrolled study participants to have sufficient power to detect between group differences, but will plan to increase enrollment (N=120 total participants) to account for data integrity issues in a small number of participants.

*Missing Data and Attrition.* In order to minimize missing data and study attrition, enhanced communication between research staff and participants will be emphasized. However, these methods do not ensure that all data will be collected and appropriate analysis methods will be employed to accommodate missing data. In keeping with the ITT principle, we will make every effort to continue assessments for the entire course of treatment, even among those who fail to adhere to randomized assignment or stop participating in the study assigned intervention.

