#### c. Potential Risks

##### Adverse events related to study medication

The informed consent process will be used to thoroughly educate participants about potential medication-related risks. Rigorous screening procedures and exclusion criteria are designed to exclude potential participants at elevated risk for adverse events. Specifically, study research staff will carefully assess adverse events with participants at each study visit and will contact the medical clinician immediately with any concerns. Research staff will also review the participant-completed Beck Depression Inventory at each visit. If the BDI results suggest deterioration with depression or other psychiatric conditions, a more comprehensive assessment will be completed, with careful plan to address symptoms (e.g., discontinuation of study medication if indicated, referral for psychiatric treatment if indicated, development of safety plan if indicated, etc.). The study PI and medical clinician will be immediately contacted in the event of acute concerns and will guide the plan for addressing and managing presenting symptoms. Participants will have access to the study physician 24 hours, 7 days a week for emergencies. Participants experiencing intolerable adverse events will have the opportunity to reduce dose or discontinue medication altogether, while remaining in the study for ongoing monitoring. Urine pregnancy tests will be conducted weekly throughout treatment for female participants.

Though detailed safety plans are in place for study participants, no serious or severe adverse events or

interactions are expected to occur with NAC. Adverse events related to this medication (e.g., allergic reaction, decreased appetite, gastrointestinal discomfort) are possible and will be assessed carefully throughout the study.

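### Three termination rules end study participation as well as medication, so some obtainable Week 8 outcomes would be scored as smoking

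*Combined protocol and SAP*

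**What the plan says.** All references are to the combined protocol and SAP.

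- **Section E.5, Data and Safety Monitoring Plan.** The list of seven reasons begins "Circumstances requiring that a patient be terminated from the study are as follows". Reason (1), intolerable side effects, carries a softening clause: "though we will encourage participants to remain in the study without medication". Reasons (2), illness that prevents taking the drug, (6), "Failure to report for medication assessment within fourteen days of the scheduled visit", and (7), pregnancy, carry none. A closing sentence covering every case promises "every effort to manage the participant and collect appropriate adverse event outcome data". Smoking status is not mentioned.
- **Section D, Missing Data and Attrition.** Under the ITT principle, staff are to make every effort to keep assessing people through the whole treatment course, "even among those who fail to adhere to randomized assignment or stop participating in the study assigned intervention".
- **Section D, Statistical Analyses.** In the ITT analysis "participants will be deemed not-abstinent at any missed visit or missing CO measure", and drop-out is expressly included. Confirmed abstinence at Week 8 needs both breath CO and urine cotinine.
- **Off-drug follow-up elsewhere.** Section D (Weekly Study Visits) keeps following people who cannot tolerate the reduced dose. Section E.1.c lets those with intolerable adverse events "discontinue medication altogether, while remaining in the study for ongoing monitoring", and for psychiatric deterioration it lists "discontinuation of study medication if indicated" among the options. Neither section covers (2), (6) or (7).

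**The concern.** Someone too ill to swallow capsules, or who becomes pregnant, has stopped the intervention. The missing-data paragraph says to keep assessing that person; the termination list says to end participation. Staff who follow the termination list would not seek a Day 56 smoking outcome, and the analysis rule would then record a smoker.

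Aim 3 exists to supply Week 8 effect sizes for a later trial, so misclassification created by the protocol's own rule bears on that purpose. The planned modified ITT, per-protocol and completer analyses show how far results depend on missing data, but they cannot recover outcomes nobody tried to collect. The 20% attrition allowance under Power and Sample Size (110 x 0.20 = 22 people) protects sample size; it does not affect how these people are scored.

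**Working it through.** **1. Does termination mean more than stopping the drug?** Section E.5 provides separately for stopping medication because of adverse experiences or marked deterioration. Reason (1) also distinguishes being in the study from being on medication. So for (2), (6) and (7) the natural reading is that participation ends.

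**2. When can reason (6) act?** Visits fall weekly from Day 7 to Day 56; nominal days are assumed.
- Earliest: a missed Day 7 visit runs out at Day 7 + 14 = Day 21. That is after the Day 1-3 primary outcome and 56 - 21 = 35 days before Day 56.
- Latest that matters: a missed Day 35 visit runs out at Day 49. Someone who also missed Days 42 and 49 but would have come on Day 56 has already been terminated.
- A missed Day 42 visit runs out at Day 42 + 14 = Day 56, so a person who attends on Day 56 has reported in time.

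**3. The plan's own Week 8 figure.** The plan states a detectable difference of 23-29 points with 88 completers (44 per arm) and placebo abstinence of 10-30%. With an unpooled two-proportion test, two-sided 5% (sidedness assumed), power is 0.781 for 10% v 33% and 0.816 for 30% v 59%. The pooled version gives 0.756 and 0.792. The stated range is reproduced to within rounding and choice of formula, and is not disputed. It is a detectable difference, used below only as a scale.

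**4. Direction of the effect (hypothetical).** Let s0 and s1 be the shares of the placebo and NAC arms terminated under (2), (6) or (7) whose Week 8 status could have been obtained. Assume they abstain at their arm's rates, p0 and p1, and ignore other missing data.

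Scored difference = p1(1 - s1) - p0(1 - s0)

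| s1 (NAC) | s0 (placebo) | 10% v 33% (true 23.0) | 30% v 59% (true 29.0) |
|---|---|---|---|
| 2% | 2% | 22.5 | 28.4 |
| 5% | 5% | 21.9 | 27.6 |
| 10% | 10% | 20.7 | 26.1 |
| 10% | 2% | 19.9 | 23.7 |
| 2% | 10% | 23.3 | 30.8 |

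With equal shares the difference shrinks by the factor 1 - s. With unequal shares it can fall further (by 23.0 - 19.9 = 3.1 and 29.0 - 23.7 = 5.3 points in the fourth row) or rise (last row). Equal shares of 2-10% are about 2-11 of 110 people; 11 would be half of the 22 allowed for all attrition.

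**5. Do the planned sensitivity analyses settle it?** Suppose 10% of each arm is terminated, these people are half as likely to be abstinent, and there is no other missing data. If q is the abstinence rate in the remaining 90%, the true rate is 0.90q + 0.10(0.5q) = 0.95q.
- ITT difference: 23 x 0.90/0.95 = 21.8; 29 x 0.90/0.95 = 27.5.
- Completer difference: 23/0.95 = 24.2; 29/0.95 = 30.5.

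The two bracket the true 23 and 29, and neither returns them. The ITT loss here is 1.2 and 1.5 points, about half the 2.3 and 2.9 in the equal 10% row, so the result also depends on how terminated people would have fared.

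**The case against.** The strongest reply is that the termination phrase is used loosely. Reason (1) sits in the same list, yet those people are encouraged to stay. Nothing in Section E.5 forbids a smoking assessment, and a safety section would naturally name adverse event data. The missing-data paragraph could be taken to govern. For pregnancy, the wording under Randomization and Weekly Visit Assessments is conditional: the test helps decide whether a woman should be terminated.

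Part of this stands. A reader might infer that the protocol prohibits Week 8 assessment after termination; it does not say so. But an explicit exception for (1) alone makes the silence on the others harder to dismiss, and nothing extends off-drug follow-up to (2), (6) or (7). The conflict remains.

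Four further objections reduce the weight:

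- Reason (6) requires three consecutive missed weekly visits, and remote visits are available for scheduling conflicts. It mostly describes people already lost to contact, who would be missing under any wording.
- Pregnancy should be rare, because it is an exclusion at entry and birth control is required.
- Counting missing as smoking is pre-specified. That rule is not at issue here; the point is avoidable missing data.
- Remote or diary data would not change the ITT score, because the CO measure would still be missing. Only clinic attendance would.

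**Conclusion.** The inconsistency is real and worth correcting, as a cheap improvement and not as a threat to the trial. It rests on reading the termination list as written and on some terminated people being willing to attend on Day 56. That is most plausible for (2) and (7), and for (6) only where contact resumes.

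The effect falls on Aim 3. Its size is unknown and probably small, and every points figure above is hypothetical.

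Several stronger inferences are not supported:

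- **A ceiling on the loss.** A reader might take the 2.3-2.9 points lost in the equal 10% case as a maximum. It holds only for equal shares of at most 10%; the 10% v 2% case already exceeds it.
- **A consistent bias against NAC.** That needs equal termination between arms; otherwise the direction is open.
- **Damage to the primary outcome.** Reason (6) cannot act before about Day 21, and (2) or (7) would rarely arise within Days 1-3.
- **A quantified effect on relapse (Aim 2).** The plan does not say how a terminated participant enters that analysis.
- **The same fault in (3)-(5).** Psychiatric crisis, hospitalization and incarceration raise clinical and feasibility questions that statistics do not decide.

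**What to change.** Reword the termination paragraph in Section E.5 so that (2), (6) and (7) end study medication only, as Section D already does for intolerance. State that smoking status will still be sought at Days 56 and 84 unless consent is withdrawn, by clinic visit with breath CO and urine cotinine. Where a visit is impossible, collect diary data, a remote contact or an offsite urine sample, and use these only in the planned sensitivity analyses, leaving the ITT scoring rule unchanged. For (3)-(5), continue smoking assessment where clinically appropriate and feasible.

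The cost is one paragraph and some extra contacts or visits: about 2-11 people at the assumed 2-10%, with little gained for those under (6) who cannot be reached.
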